STUDY PROTOCOL AND STATISTICAL ANALYSIS PLAN

Official title: Furoscix in Heart Failure Patients with Diuretic Resistance

NCT number: NCT05528588

IRB Approved date: 07-22-24

Form A

IRB #

STU-2022-0768

PROTOCOL FORM / RESEARCH DESCRIPTION

If an item does not apply to your research project, indicate that the question is "**not applicable**" – do not leave sections blank

Click once on the highlighted entry in each box to provide your response. Click the item number/letter or word, if hyperlinked, for detailed instructions for that question. If your response requires inserting a table, picture, etc, you may need to first delete the box that surrounds the answer and then insert your table or other special document.

1. Purpose and objectives. *List the purpose and objectives:*

The purpose of this study is to assess the diuretic efficiency of subcutaneous furosemide (Furoscix) compared to oral diuretic therapy for patients post heart failure (HF) hospitalization and evaluate the impact of diuretic resistance as identified by the BAN-ADHF (Blood urea nitrogen, creatinine, Natriuretic Peptide levels, Atrial fibrillation, Diastolic blood pressure, Hypertension and Home diuretic dose, and Heart Failure hospitalization) risk score.

Key Outcomes:

1. Post-treatment urine output over 8 hours. This will be assessed in mL per mg of treatment (Furoscix vs. oral diuretic).
2. Post-treatment urine sodium. Urine sodium will be assessed hourly over 8 hours post-treatment.

Safety Outcome Measures:

1. Number of participants with post-intervention need for emergency department visit or hospitalization. The count of participants with post-intervention need for emergency department visit or hospitalization for worsening heart failure is assessed.

Goals: Successful completion of this project will establish proof of concept that Furoscix provides more effective post-hospitalization diuresis than the traditional oral dose in a diuretic resistance patient population. This study will provide pilot data to guide the design of larger studies involving a diuretic-resistant heart failure population.

2. Background.

- Describe past experimental and/or clinical findings leading to the formulation of your study.
- For research involving investigational drugs, describe the previously conducted animal and human studies.
- For research that involves FDA approved drugs or devices, describe the FDA approved uses of this drug/device in relation to your protocol.

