If patients still meet all eligibility criteria and sign informed consent, they will undergo stratified randomization based on BAN-ADHF score (≥ 12 vs. < 12). Within each stratum, patients will be randomized in a 1:1 ratio (intervention: control) during the research visit. Patients will be informed via telephone prior to visit to not take home oral dose of diuretic on the day of the visit and will be instructed to hold any caffeine products such as coffee or any other drugs that could increase urine output on the day of the visit.

- **Intervention: Furoscix** – administration of subcutaneous furosemide (Furoscix) during study visit. It will be administered using the Furoscix Infusor. Per information from the Sponsor, "The Infusor is placed on the patient's abdomen for subcutaneous infusion. Furoscix is delivered subcutaneously through a small, 27-gauge, 6 mm needle. The Infusor is preprogramed to deliver 80 mg (10 mL) furosemide over 5 hours using a biphasic delivery profile of 30 mg furosemide (3.75 mL) over the first hour and 12.5 mg furosemide (1.56 mL) per hour over the subsequent 4 hours."
- **Control: Oral Diuretic** - administration of oral diuretic during study visit. Patients will bring their home prescription of oral diuretic and will take the oral formulation while in the visit. If the patient did not bring their home dose, an equivalent oral dose will be provided from the UT Southwestern Investigational Drug Service.

The intervention arm (Furoscix over 5 hours at 8 mg/mL) will be compared to a usual care group (home oral diuretic dose prescribed by discharge physician). Patients will be monitored for 8 hours in the Clinical Research Unit post-drug administration for clinical safety and to measure clinical response.

Other research procedures:

- Patients will be instructed to void immediately before dosing (pre-dose urine) and this sample will be discarded. After medication administration, urine from spontaneous voids during post-dose phases will be collected and recorded. Urine sodium measurements will be obtained at hourly intervals. Urine from each collection period must be refrigerated until the end of the collection period. Total volume of urine produced will be assessed over 8 hours post-study drug administration. 5 mL of each hourly urine sample will be sent for a urine sodium lab test in a yellow round bottom tube.

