- Collect approximately 10 mL of blood for a blood test to check patient's electrolytes. This will be done at the end of the research visit.
- Call participants in 7 days after their research visit to assess if patient has had a presentation to urgent care, emergency department, or is re-hospitalized for acute exacerbation in heart failure.

Compensation:

To account for a full day of research monitoring, patients will be compensated \$250 for their participation in the study with the UTSW ClinCard.

Data Safety and Monitoring:

Patient safety will be tracked over the study. For any adverse events (AE) that occur during their participation in the study, medical care will be provided and patients will be followed until resolution. See Form D for more details.

Form A

IRB #

STU-2022-0768

Privacy and Confidentiality:

To protect patient's privacy and confidentiality, we will ensure the consent process takes place in a private area and conduct research in secure areas where others will not have access to their PHI. All PHI collected during the study will be coded with a Subject ID using a randomized code. The key to the code will be kept on a password database in the research coordinator's locked office. Only authorized personnel listed on Form B will have access to the data. Any hard copy documents such as the signed consent form will be kept in the research coordinator's locked office.

Statistical Analysis:

This study will assess the primary outcomes of greater diuretic efficiency as measured by total urine output and urine sodium. As the Furoscix group will receive 80 mg of subcutaneous furosemide and the control group will take a home dose of oral diuretic, urine output will be normalized per mg of treatment administered. Differences in total urine produced will be compared between Furoscix versus oral diuretic groups. The urine sodium will be assessed hourly, and will be compared across the two groups.

As this study is a preliminary pilot study to assess the effect of Furoscix on diuretic efficacy, we have chosen a convenience sample of 70 patients to allow for a comparison between patients who receive Furoscix and those who do not receive Furoscix. The results of this trial will serve as a precursor for a larger, multicenter trial of Furoscix in patients with diuretic resistance.

4.b. List of the study intervention(s) being tested or evaluated under this protocol

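### Urine output is scaled per mg because the arms' doses differ, but urine sodium, the paired primary outcome, is given no dose scale, unit or 8-hour summary

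*Combined protocol and SAP*

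**What the plan says.** The Statistical Analysis text in section 4.a opens: "This study will assess the primary outcomes of greater diuretic efficiency as measured by total urine output and urine sodium". It then gives the reason for scaling, "As the Furoscix group will receive 80 mg of subcutaneous furosemide and the control group will take a home dose of oral diuretic", and applies it to one outcome: "urine output will be normalized per mg of treatment administered". A further sentence says that differences in total urine will be compared between groups, without saying whether this is the raw or the scaled quantity. Sodium follows: "The urine sodium will be assessed hourly, and will be compared across the two groups".

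Key Outcomes in section 1 shows the same asymmetry. Urine output is to be expressed in mL per mg of treatment. For sodium the entry reads "Urine sodium will be assessed hourly over 8 hours post-treatment", with no denominator.

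On measurement, the research procedures in section 4.a say "5 mL of each hourly urine sample will be sent for a urine sodium lab test in a yellow round bottom tube". Spontaneous voids are collected and recorded, and total volume is assessed over 8 hours. The Furoscix dose is fixed: "The Infusor is preprogramed to deliver 80 mg (10 mL) furosemide over 5 hours". Controls take their own prescribed home dose, for which no mg value or range is given. The background in section 2 names furosemide and torsemide as the standard oral drugs, and no conversion between them is given for the analysis.

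**The concern.** The reason given for scaling urine output is a difference between the arms, so it applies equally to any other measure of response to the same doses. The plan applies it to one of two outcomes that it says measure the same property, and does not explain why.

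The stated purpose is diuretic efficiency, which is a per-mg claim. The stated goal is to show more effective diuresis than the usual oral dose, which is a per-treatment claim. As written, the sodium outcome does not address the first and the mL/mg outcome does not address the second, so neither claim is supported by both primaries. If the two disagree, part of the disagreement will come from the home doses enrolled, and the plan gives no way to separate that part. The results are meant to guide a larger trial, so the ambiguity would carry forward.

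**Working it through.** The plan states no effect size, SD, alpha or power, and the 70 patients are a convenience sample, so there is no sample-size figure to reproduce. The infusor dose is consistent: 30 + 4 × 12.5 = 80 mg.

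**Inputs.** From the documents: 80 mg in the Furoscix arm; 70 patients randomised 1:1, so about 35 per arm. Assumed, because the documents give none: a single control dose D of 20, 40, 80, 120 or 160 mg, and a between-patient log-SD s of 0.4 to 0.8.

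**Case A: sodium as an amount excreted.** Let R be the true Furoscix/control ratio of 8-hour totals, taken as the same for urine and sodium.

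- Sodium ratio without a dose scale = R
- mL/mg ratio = (R/80) ÷ (1/D) = R × D/80

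The two point in opposite directions when R lies between 1 and 80/D.

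| D (mg) | Sodium ratio, R = 1 | mL/mg ratio, R = 1 | R for which the two conflict |
|---|---|---|---|
| 20 | 1.0 | 0.25 | 1 to 4.0 |
| 40 | 1.0 | 0.50 | 1 to 2.0 |
| 80 | 1.0 | 1.00 | none |
| 120 | 1.0 | 1.50 | 0.67 to 1 |
| 160 | 1.0 | 2.00 | 0.5 to 1 |

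Example: with R = 1.5 and D = 40, sodium reads 1.50 (favours Furoscix) and mL/mg reads 1.5 × 40/80 = 0.75 (favours control).

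**Would this show with 35 per arm?** Suppose true volumes are equal and the test is two-sided at 0.05 on the log scale. The chance that mL/mg differs significantly through dose alone is approximately Φ(|ln(D/80)| / (s√(2/35)) − 1.96).

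- D = 40 or 160: |ln(D/80)| = 0.693. At s = 0.8 this is Φ(3.62 − 1.96) = 0.95; at s = 0.4 it is 1.00.
- D = 120: |ln(D/80)| = 0.405. At s = 0.8 this is Φ(2.12 − 1.96) = 0.56; at s = 0.4 it is 0.99.

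A comparison of equal sodium amounts would be significant about 5% of the time.

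**Case B: sodium as a concentration.** Amount excreted = concentration × volume. Two patients with the same concentration and a twofold difference in volume differ twofold in sodium excreted, and a concentration comparison shows no difference. The ratios in the table do not carry over. Dividing a concentration by mg would not give an efficiency either, because volume has to enter first.

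**After the fix.** With sodium as mmol excreted, the mmol/mg ratio is R × D/80, the same as for mL/mg, and the undivided ratios are both R. The gap due to dose disappears on either scale.

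**The case against.** Several points on the other side stand and limit the claim.

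- A reader might infer that the plan prescribes an undivided sodium comparison. It does not; it is silent. The per-mg rule stated for urine output alone makes undivided the natural reading, but the supportable defect is an unspecified scale.
- The 5 mL aliquot sent to the laboratory most naturally yields a concentration. The ratios in the working hold only if that is converted to an amount.
- A reader might infer that sodium without a dose scale favours Furoscix whenever the home dose is below 80 mg. That needs response proportional to mg (equal per-mg efficiency would give 80/D), and the documents give no dose-response data.
- A reader might also infer that agreement or conflict between the primaries reflects the home doses and not the drug. This does not follow: R enters both ratios, so both respond to treatment and dose is an added contribution.
- The sentence on total urine may already mean raw volume. If so, urine output has both scales, but sodium still has no per-mg counterpart and no defined unit.
- Adding a per-mg sodium result brings in a denominator that mixes furosemide and torsemide mg, so the denominator has to be defined as well.

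It can also be said that this is a pilot with no test or success rule, so no stated decision depends on the two outcomes agreeing. That lowers the stakes but does not remove the problem: the outcomes are called primary and the remedy needs no extra patients, visits or assays.

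**Conclusion.** The concern holds in this form: two outcomes presented as measures of one property are not on a common scale. The plan's own reason for scaling is applied to only one of them, and the other lacks a unit, an 8-hour summary and a dose scale. Nothing elsewhere in the documents repairs this.

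If sodium is an amount excreted and 8-hour totals are equal, the two primaries differ by the factor home dose/80, from 0.25 to 2.0 over assumed doses of 20 to 160 mg, and match only at 80 mg. The actual size depends on the home doses enrolled, which the documents do not give. If sodium is a concentration, those figures do not apply, and the outcome supports neither a claim about total sodium excretion nor one about efficiency. In neither case do the documents show that dose alone would decide the result. The change should be made before analysis.

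**What to change.** Amend the Statistical Analysis text and Key Outcomes as follows.

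1. Define the sodium outcome as 8-hour sodium excreted in mmol: the sum over collections of concentration × volume, with the volume recorded for each collection.
2. Report two pairs: mL with mmol, and mL/mg with mmol/mg. State that the comparison of total urine refers to raw mL.
3. Use one prespecified furosemide-equivalent mg denominator for both per-mg outcomes, with the torsemide conversion stated as an assumption. This is for analysis only and does not affect what patients take.
4. State that a claim of greater efficiency rests on the per-mg pair, and a claim of more effective diuresis on the undivided pair.

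The cost is low. Sodium samples and post-dose urine are already collected. The protocol commits explicitly only to an 8-hour total volume, so a volume for each collection must be recorded if it is not already. The other costs are stating an equivalence assumption and reporting two more comparisons.
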